10.2 Baseline/Randomization (Visit 2, Week 0/Beginning of Titration)

The following activities will take place at Visit 2A (first day of 2-day visit):

- Assess inclusion/exclusion criteria (applicable criteria referencing the baseline visit);
- Obtain body weight;
- Obtain vital signs (blood pressure, heart rate, respiration rate and temperature);
- Record any adverse events reported or observed;
- Record any changes in concomitant medications;
- Perform a urine pregnancy test (WOCBP only) and remind subject about contraception. If the subject is pregnant, she will not qualify for the study;
- Set up 24-hr ABPM monitoring equipment, and initiate monitoring;
- Provide subject with instructions for proper handling of ABPM device and remind the subject to return to the clinic in 24 hours to complete evaluation.

The following activities will take place at Visit 2B (second day of 2-day visit):

- Record any adverse events reported or observed;
- Record any changes in concomitant medications;

- End 24-hr ABPM monitoring, disconnect devices, and upload data;
- Contact EDC/RTSM to obtain randomization assignment for subject upon verifying successful ABPM; if verification of successful ABPM cannot be made, repeat 24-hr ABPM setup as described for Visit 2A and bring subject back in 24 hours to complete evaluation;
- Dispense study drug and instruct the subject to take one capsule every morning (with or without food) in the order indicated on the blister card ([Section 9.4.3](#)) and advise on lifestyle counseling. Subject should also be instructed to withhold dosing on the morning of the next scheduled study visit; and
- Schedule the next study visit in 4 weeks (28 ± 3 days).

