10.4 Week 8/End of Study or Early Termination (Visit 4)

The following activities will take place at Visit 4A (first day of 2-day visit):

- Obtain body weight;
- Obtain vital signs (blood pressure, heart rate, respiration rate and temperature);
- Collect PK blood sample for assessment of phentermine and topiramate levels (prior to dosing);
- Record any adverse events reported or observed;

- Record any changes in concomitant medications;
- Perform a urine pregnancy test (WOCBP only) and remind subject about contraception;
- Set up 24-hr ABPM monitoring equipment;
- Collect study drug from previous visit, assess treatment compliance, and perform drug accountability;
- Administer last daily dose of study drug, record time of dosing, then initiate ABPM monitoring; and
- Provide subject with instructions for proper handling of ABPM device and remind the subject to return to the clinic in 24 hours to complete study.

The following activities will take place at Visit 4B (second day of 2-day visit):

- Record any adverse events reported or observed (note that as described in [Section 12.3](#) adverse events known to the investigator and occurring within 28 days after the last dose of study drug must be reported);
- Record any changes in concomitant medications;
- Perform a physical examination;
- End 24-hr ABPM monitoring, disconnect devices, and upload data upon verifying successful ABPM; if verification of successful ABPM cannot be made, repeat 24-hr ABPM setup as described for Visit 4A and bring subject back in 24 hours to complete evaluation;
- Perform 12-lead electrocardiogram (ECG);
- Obtain full blood chemistry, hematology, and urinalysis for laboratory testing;
- Obtain vital signs (blood pressure, heart rate, respiration rate and temperature); and
- Discontinue subject's study participation.

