11.3 Vital Signs

Vital signs (systolic blood pressure, diastolic blood pressure, heart rate, respiration rate, temperature) will be assessed at Screening, Randomization, Week 4, and Week 8/end of study or early termination. Subjects should be seated comfortably for at least 10 minutes prior to assessing vital signs. Heart rate and respiratory rate measurements should be made by counting events (heartbeats or breaths) for a period of 30 seconds and multiplying these values by 2 to obtain the rates per minute. A calibrated blood pressure monitor should be employed for blood pressure measurements. The same cuff should be used for the same subject across multiple visits when blood pressure is performed. The same person should perform all assessments for a given subject.

Clinic blood pressure for determining hypertension should be the average of three successive BP readings, collected at least 2 minutes apart. The mean of the three values will be recorded as the subject's blood pressure.

11.4 24-hr Ambulatory Blood Pressure Monitoring (24-hr ABPM)

At Baseline and at Week 8/end of study or early termination, 24-hr ABPM will be performed non-invasively using a validated oscillometric monitor provided by a central vendor. Blood pressure and heart rate will be measured every 20 minutes from 6:00 to 22:00 hours, and every 30 minutes from 22:01 to 5:59 hours for 24 consecutive hours, while subjects continue normal routine activities. The monitor will be attached in the morning and removed after at least 24 hours. Data will be uploaded to a computer at the end of the recording session and prior to discharging the subject from the study visit, site staff will review the data to assure that: (1) at least 80% of the readings are valid, (2) there are at least 24 hours of data, and (3) there are no more than two consecutive hours of missing data. If any of these criteria are not satisfied, subjects will be asked to repeat the assessment for an additional 24 hours. ABPM hook up will be done by qualified staff.

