	Tributary	Within-treatment group comparison (effect at Week 8 minus the value at baseline): ✓ LSM for the within-group difference ✓ 95% CI of the LSM ✓ p-value

The following SAS programming codes will be applied:

```
PROC MIXED DATA=DATAIN;
  CLASS TREATMENT(REF='Placebo' [or 'Phentermine']) SEX AGE HYPSTATUS;
  MODEL CHG_SBP=TREATMENT SEX AGE HYPSTATUS BASE_SBP/SOLUTION DDFM=KR;
  LSMEANS TREATMENT/ALPHA=0.05 PDIFF CL;
```

RUN;

For subjects who discontinue from the study but complete Early Termination ABPM assessments, such measurements will be mapped to Week 8/End of Study or Early Termination for analysis. For subjects who have missing 24-hr SBP measurements at baseline or at Week 8 after mapping unscheduled visits, missing data will be imputed using the approach below. If the percentage of missing readings at either visit is $\leq 25\%$ (see [Section 5.4](#)), 24-hr mean SBP values will be calculated by taking the average of non-missing and imputed measurements over the 24-hr time period. Imputed measurements will be derived as follows:

1. For any intermediate missing observations between two non-missing readings BP_1 and BP_2 , missing observations will be imputed using the formula: $BP = (BP_2 - BP_1)/(t_2 - t_1) \times (t - t_1) + BP_1$; whereas t_1 , t , and t_2 are the time of the measurements respectively;
2. If missing observations are at the beginning or at the end, the beginning observations will be imputed as the average of non-missing and step 1 imputed data points from 6:00 to 22:00 hours. The end observations will be imputed similarly using data points from 22:01 to 5:59 hours.

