7.2.1.1 Sensitivity Analyses of Primary Endpoint

[figure not shown]
The following sensitivity analyses will be conducted on the ITT Population to evaluate the robustness of the primary analysis results and the effect of missing data for the primary endpoint:

Missing at Random (MAR) based Multiple Imputation (MI)

Step 1: If the percentage of missing 24-hr SBP readings at baseline or at Week 8 is $\leq 25\%$, such missing subject data will be imputed using the approach specified in [Section 7.2.1](#). The 24-hr mean SBP value will be calculated by taking the average of non-missing and imputed measurements over the 24-hr time period.

Step 2: If the percentage of missing 24-hr SBP readings at baseline or at Week 8 is $> 25\%$, MAR-based MI approach with Fully Conditional Specification (FCS) Regression will be applied to impute the 24-hr mean SBP value using Step 1 calculated 24-hr mean SBP values.

[figure not shown]
Example SAS programming codes are:

The ANCOVA model will be examined for each set of data. The results from the 50 sets of

data will be combined via Rubin's rule to produce estimated LSMS and 95% CIs that incorporate the uncertainty from missing data. PROC MIANALYZE will be used.

Example SAS programming codes are:

[figure not shown]

Two-way Tipping Point Analysis

An additional sensitivity analysis using 2-way tipping point strategy¹ will be conducted on Step 2 above to explore the influence of missing data for 1) VI-0521 versus placebo; 2) VI-0521 versus phentermine on the overall conclusion of statistical inference. In this approach, a wide spectrum of assumptions regarding the magnitude of missingness (from less conservative to more conservative) is proposed for replacing missing data. The goal is to find a 'tipping' point from among these assumptions under which the study conclusions shift from being favorable to VI-0521 to being unfavorable. After such a tipping point is determined, clinical judgment can be applied as to the plausibility of the assumptions underlying this tipping point. The tipping point can be identified when the result is no longer statistically significant.

To conduct this analysis, the PROC MI procedure will be used with additional “shift” parameters to account for missing not at random (MNAR). The shift parameters will be added using MNAR ADJUST syntax.

Example SAS codes for this MI procedure are:

A large black rectangular box redacting a block of SAS code.

SHIFTPARAM1

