SHIFTPARAM2), the MI procedure outlined above will be executed. ANCOVA analysis will be run on all imputed datasets. Confidence intervals of the between-treatment comparisons estimated from the PROC MIANALYZE will be reported. The following shift parameters will be identified:

1. For non-inferiority: when the upper bound of the two-sided 95% confidence interval just crosses 3 mmHg;
2. For superiority: when the upper bound of the two-sided 95% confidence interval just crosses 0 mmHg.

Analysis of Missing Data Pattern

Number and percentage of subjects with at least 75% of non-missing 24-hr ABPM readings at baseline and Week 8 will be summarized by the following variables on the ITT Population:

- Baseline mean SBP as measured by 24-hr ABPM (< population median and \geq population median);
- Baseline mean DBP as measured by 24-hr ABPM (< population median and \geq population median);
- Sex (male and female);
- Age (< 50 and \geq 50 years);
- Race (white and not white);
- Hypertensive status (no medical diagnosis of or treatment for hypertension; medical diagnosis of hypertension treated with 0-2 antihypertensive agents; or medical diagnosis of hypertension treated with 3 or more antihypertensive agents).

Number and percentage of subjects with more than two consecutive hours of missing 24-hr ABPM readings will also be summarized by visit on the ITT Population.

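### The SAP fills missing readings at the end of a 24-hour recording with the night average, although readings due from 06:00 onward are morning readings

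*SAP*

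**What the plan says.** SAP 7.2.1 allows reading-level imputation when at most 25% of a recording's readings are missing. Step 1 interpolates gaps between two observed readings. Step 2 deals with gaps at either end. Missing readings at the beginning get the subject's 06:00-22:00 average. For the other end the text is: "The end observations will be imputed similarly using data points from 22:01 to 5:59 hours". Neither step 2 nor SAP 7.1.4 adds a condition on the clock time of the missing reading.

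Protocol 11.4 fixes when a recording runs: "The monitor will be attached in the morning and removed after at least 24 hours". Sites must also check that "at least 80% of the readings are valid", that there are 24 hours of data, and that "there are no more than two consecutive hours of missing data"; otherwise the recording is repeated.

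The fill is used beyond the primary analysis. Step 1 of the ITT sensitivity analysis (SAP 7.2.1.1) says that for recordings with at most 25% missing, "such missing subject data will be imputed using the approach specified in" Section 7.2.1. SAP 7.2.2 uses a similar method for 24-hour diastolic pressure.

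**The concern.** A recording that starts in the morning ends the next morning. The rule therefore suits missing end readings due before 06:00, but not those due between 06:00 and hook-up time. Those are morning readings, and they are given a night value. In a subject whose pressure falls at night this pulls the 24-hour mean down.

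The most exposed analysis is the ITT sensitivity analysis. It has no minimum recording length, and no ITT analysis without imputation stands beside it to show an artefact: the observed-case analysis in SAP 7.2.1.2 is per-protocol only. The missing-pattern summary ("Number and percentage of subjects with more than two consecutive hours of missing 24-hr ABPM readings will also be summarized by visit") counts gaps but leaves the means as they are. An analysis meant to test the effect of missing data should not add an avoidable error to the recordings that have missing data.

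**Working it through.** **Reading grid (SAP 7.1.4).** 06:00-22:00 every 20 minutes gives 49 readings, and 22:30-05:30 every 30 minutes gives 15, so 64 in total. 0.75 x 64 = 48, which reproduces the count in SAP 5.4. The 25% limit is 16 readings.

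**End readings due at 06:00 or later, by start time.** 07:00: 3; 08:00: 6; 09:00: 9; 10:00: 12. The documents give no hook-up time, so these starts are assumptions.

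**Assumed profiles.** The day-night systolic difference D is not in the documents; I take 15 mmHg, with a range of 10-20. Two noise-free shapes are used: two-level (day level 06:00-22:00, night level otherwise), and linear (day level 07:30-21:30, night level 00:00-05:00, straight lines between).

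**Worked case: 09:00 start, 06:00-08:40 lost (9 of 64), D = 15.** Values are deviations from the day level.

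*Two-level*
- SAP fill: -9 x 15/64 = -2.11.
- Unfilled: true mean -15 x 15/64 = -3.52; observed mean -15 x 15/55 = -4.09; error -0.58 (from unrounded values).
- Clock-window fill: 0.

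*Linear*
- The nine lost readings sum to -9 - 7 - 5 - 3 - 1 = -25. The 15 night readings sum to -204, mean -13.6. The 40 remaining day readings sum to -4, mean -0.1.
- SAP fill: (9 x -13.6 + 25)/64 = -97.4/64 = -1.52.
- Unfilled: -208/55 + 233/64 = -0.14.
- Clock-window fill: (9 x -0.1 + 25)/64 = +0.38.

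Over D = 10-20 the SAP fill errs by -1.41 to -2.81 (two-level) and -1.01 to -2.03 (linear).

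**Other cases at D = 15 (error in mmHg)**

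| Start, readings lost | Profile | SAP fill | Unfilled | Clock-window |
|---|---|---|---|---|
| 08:00, 6 | two-level | -1.41 | -0.36 | 0 |
| 08:00, 6 | linear | -0.88 | +0.05 | +0.38 |
| 10:00, 12 | two-level | -2.81 | -0.81 | 0 |
| 10:00, 12 | linear | -2.16 | -0.36 | +0.37 |
| 07:00, 16 | two-level | -0.70 | +2.89 | 0 |
| 07:00, 16 | linear | +1.41 | +3.16 | +1.75 |

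In the last two rows the loss runs back into the night. The SAP fill then beats no imputation, and under the linear profile its error is positive. The sign also turns if night pressure exceeds day pressure: with night 5 mmHg higher (09:00, 9 lost) the SAP fill errs by +0.7 (two-level) or +0.5 (linear).

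**Whole grid (4 starts x 1-16 lost x 2 profiles = 128 cases).** The SAP fill is further off than the clock-window fill in 112 and further off than no imputation in 96. In the 60 cases where only morning readings are lost, the counts are 59 and 60.

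**Per-protocol exposure.** The 64 readings span 23 h 40 min. If the 23.5-hour rule in SAP 5.4 means span, one lost end reading leaves 23 h 20 min and fails. With a closing reading at 24 hours, one lost passes and two fail. One lost reading costs 0.09-0.31 mmHg over D = 10-20.

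**Site check on the worked case.** 55/64 = 85.9% valid passes the 80% rule, but the 24-hour and two-hour rules fail, so a repeat is due.

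**Between-arm effect.** The shift times the difference between arms in the share of affected recordings. For an assumed 5 points: 0.05 x 1.01 to 0.05 x 2.81 = 0.05-0.14 mmHg. If the shares are equal, it is zero.

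**The case against.** The strongest objection is that no decision is shown to depend on this. The confirmatory tests use the per-protocol population, where about one end reading can be affected. The planned standard error of a treatment difference is 10 x sqrt(2/185) = 1.04 mmHg, so 0.05-0.14 mmHg is about 5-13% of it, and under 5% of the margin. A 5-point imbalance is generous, since it equals the whole planned drop-out rate. A recording like the worked case should have been repeated. At baseline the step is "Contact EDC/RTSM to obtain randomization assignment for subject upon verifying successful ABPM", and at Week 8, "if verification of successful ABPM cannot be made, repeat 24-hr ABPM setup as described for Visit 4A". All of this stands. Affected recordings would mostly be Week 8 or early-termination recordings whose repeat failed or was not done, and the documents give no evidence that these differ by arm.

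Second, the proposed rule is not always best. Its exact zeros come from the two-level profile, where it is right by construction. Under the linear profile it is further off than no imputation in 8 of the 60 morning-only cases, and with a 07:00 start and 3 lost it gains nothing (+0.32 against -0.31 for the SAP fill). This also stands, but it does not remove its advantage over the present rule.

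Third, beginning and end could refer to a day ordered from 06:00 to 05:59, so that lost 06:00-08:40 readings would already get the daytime average. The SAP does not say so, and step 1 treats readings in the time order of the recording. If that was the intention, step 2 still needs to state it.

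**Conclusion.** The point holds. As written, step 2 gives a night value to end readings due at 06:00 or later, which is the wrong window for any recording that starts after 06:00. When only morning readings are lost and night pressure is below day pressure, the fill biases that recording's 24-hour mean downward and does worse than no fill.

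The reading of the rule rests on the text alone. The sizes rest on an assumed day-night difference, profile and hook-up time, and they are errors in a single recording. The effect on a treatment difference needs unequal loss between arms and is small even then. The 24-hour diastolic analysis inherits the rule, though its size was not calculated. This is a low-severity correction; it gives no reason to doubt the trial's conclusions.

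**What to change.** Replace step 2 of SAP 7.2.1 with wording such as: *A missing reading at either end of a recording takes the subject's mean of the observed and step-1-interpolated readings from the clock window (06:00-22:00 or 22:01-05:59) in which the missing reading was due.* The change carries into step 1 of SAP 7.2.1.1 and the 24-hour diastolic analysis by reference. Nothing else needs to change.

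The cost is one sentence and a few lines of code. No subject is lost, and the sample size, population, model and margin are untouched. Three limits remain:
- If pressure rises gradually after 06:00, morning-only loss leaves an error of up to about +0.4 mmHg at a 15 mmHg difference.
- In 16 of the 128 cases (all linear, 07:00 or 08:00 start, nearly all with loss running into the night) the new fill is further off than the present one, by at most about 0.7 mmHg.
- Like the present rule, it has no night value to use if every night reading is lost at the end. The 25% limit allows that only for starts before 06:40.

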7.2.1.1 Sensitivity Analyses of Primary Endpoint

[figure not shown]
The following sensitivity analyses will be conducted on the ITT Population to evaluate the robustness of the primary analysis results and the effect of missing data for the primary endpoint:

Missing at Random (MAR) based Multiple Imputation (MI)

Step 1: If the percentage of missing 24-hr SBP readings at baseline or at Week 8 is $\leq 25\%$, such missing subject data will be imputed using the approach specified in [Section 7.2.1](#). The 24-hr mean SBP value will be calculated by taking the average of non-missing and imputed measurements over the 24-hr time period.

Step 2: If the percentage of missing 24-hr SBP readings at baseline or at Week 8 is $> 25\%$, MAR-based MI approach with Fully Conditional Specification (FCS) Regression will be applied to impute the 24-hr mean SBP value using Step 1 calculated 24-hr mean SBP values.

[figure not shown]
Example SAS programming codes are:

The ANCOVA model will be examined for each set of data. The results from the 50 sets of

data will be combined via Rubin's rule to produce estimated LSMS and 95% CIs that incorporate the uncertainty from missing data. PROC MIANALYZE will be used.

Example SAS programming codes are:

[figure not shown]

Two-way Tipping Point Analysis

An additional sensitivity analysis using 2-way tipping point strategy¹ will be conducted on Step 2 above to explore the influence of missing data for 1) VI-0521 versus placebo; 2) VI-0521 versus phentermine on the overall conclusion of statistical inference. In this approach, a wide spectrum of assumptions regarding the magnitude of missingness (from less conservative to more conservative) is proposed for replacing missing data. The goal is to find a 'tipping' point from among these assumptions under which the study conclusions shift from being favorable to VI-0521 to being unfavorable. After such a tipping point is determined, clinical judgment can be applied as to the plausibility of the assumptions underlying this tipping point. The tipping point can be identified when the result is no longer statistically significant.

To conduct this analysis, the PROC MI procedure will be used with additional “shift” parameters to account for missing not at random (MNAR). The shift parameters will be added using MNAR ADJUST syntax.

Example SAS codes for this MI procedure are:

A large black rectangular box redacting a block of SAS code.

SHIFTPARAM1

SHIFTPARAM2), the MI procedure outlined above will be executed. ANCOVA analysis will be run on all imputed datasets. Confidence intervals of the between-treatment comparisons estimated from the PROC MIANALYZE will be reported. The following shift parameters will be identified:

1. For non-inferiority: when the upper bound of the two-sided 95% confidence interval just crosses 3 mmHg;
2. For superiority: when the upper bound of the two-sided 95% confidence interval just crosses 0 mmHg.

Analysis of Missing Data Pattern

Number and percentage of subjects with at least 75% of non-missing 24-hr ABPM readings at baseline and Week 8 will be summarized by the following variables on the ITT Population:

- Baseline mean SBP as measured by 24-hr ABPM (< population median and \geq population median);
- Baseline mean DBP as measured by 24-hr ABPM (< population median and \geq population median);
- Sex (male and female);
- Age (< 50 and \geq 50 years);
- Race (white and not white);
- Hypertensive status (no medical diagnosis of or treatment for hypertension; medical diagnosis of hypertension treated with 0-2 antihypertensive agents; or medical diagnosis of hypertension treated with 3 or more antihypertensive agents).

Number and percentage of subjects with more than two consecutive hours of missing 24-hr ABPM readings will also be summarized by visit on the ITT Population.

7.2.1.2 Supportive Analysis of Primary Endpoint

Observed Case

The primary efficacy analysis will be repeated using only the observed case data for the PP population. The data will include any unscheduled visits that have been mapped to analysis visits using the rules outline in Table 7-1. Data will not be imputed after mapping unscheduled visits. 24-hr mean SBP values will be calculated using the non-imputed data.

